### **9.1.7 Suspected transmission of an infectious agent via a medicinal product**

For the purposes of reporting, any suspected transmission of an infectious agent via a medicinal product should be considered as an SAE; such cases must be reported immediately, recorded in the AE module of the eCRF, and followed as any other SAE. Any organism, virus, or infectious particle (eg, prion protein transmitting transmissible spongiform encephalopathy), pathogenic or nonpathogenic, is considered an infectious agent.

### **9.1.8 Overdose of investigational medicinal product**

Excessive dosing (beyond that prescribed in the protocol and including overdose) should be recorded in the eCRF. Any SAE or nonserious AE associated with excessive dosing must be followed as any other SAE or nonserious AE. These events are only considered AEs or SAEs if there are associated clinical signs and symptoms or if the act of taking the excess medicine itself is an AE or SAE (eg, suicide attempt).

### **9.1.9 Safety signal detection**

Selected data from this study will be reviewed periodically to detect as early as possible any safety concern(s) related to the IMP so that Investigators, clinical study subjects, regulatory authorities, and IRBs/IECs will be informed appropriately and as early as possible.

In addition, an independent Data Monitoring Committee (DMC) will periodically review and monitor the safety data from this study and advise UCB. Details are provided in the DMC Charter. A Cardiovascular Adjudication Committee will also periodically review and monitor the safety data from this study and advise UCB. Details are provided in the Cardiovascular Adjudication Committee Charter.

The Study Physician or medically qualified designee/equivalent will conduct an ongoing review of SAEs and perform ongoing SAE reconciliations in collaboration with the PS representative.

As appropriate for the stage of development and accumulated experience with the IMP, medically qualified personnel at UCB may identify additional safety measures (eg, AEs, vital signs, laboratory, or ECG results) for which data will be periodically reviewed during the course of the study.

## 9.2 Serious adverse events

### 9.2.1 Definition of SAE

Once it is determined that a subject experienced an AE, the seriousness of the AE must be determined. An SAE must meet 1 or more of the following criteria:

- Death
- Life-threatening  
(Life-threatening does not include a reaction that might have caused death had it occurred in a more severe form.)
- Significant or persistent disability/incapacity
- Congenital anomaly/birth defect (including that occurring in a fetus)
- Important medical event that, based upon appropriate medical judgment, may jeopardize the patient or subject and may require medical or surgical intervention to prevent 1 of the other outcomes listed in the definition of serious

(Important medical events may include, but are not limited to, potential Hy's Law [see [Section 9.5](#)], allergic bronchospasm requiring intensive treatment in an emergency room or at home, blood dyscrasias that do not result in inpatient hospitalization, or the development of drug dependency or drug abuse.)

- Initial inpatient hospitalization or prolongation of hospitalization

(A patient admitted to a hospital, even if he/she is released on the same day, meets the criteria for the initial inpatient hospitalization. An emergency room visit that results in admission to the hospital would also qualify for the initial inpatient hospitalization criteria. However, emergency room visits that do not result in admission to the hospital would not qualify for this criteria and, instead, should be evaluated for 1 of the other criteria in the definition of serious [eg, life-threatening adverse experience, important medical event].

Hospitalizations for reasons not associated with the occurrence of an AE [eg, preplanned surgery or elective surgery for a pre-existing condition that has not worsened or manifested in an unusual or uncharacteristic manner] do not qualify for reporting. For example, if a subject has a condition recorded on his/her medical history and later has a preplanned surgery for this condition, it is not appropriate to record the surgery or hospitalization as an SAE, since there is no AE upon which to assess the serious criteria. Please note that, if the pre-existing condition has worsened or manifested in an unusual or uncharacteristic manner, this would then qualify as an AE and, if necessary, the seriousness of the event would need to be determined.)

Note: Confirmed active TB is always to be considered as an SAE and must be captured on an SAE Report Form and provided to the Sponsor in accordance with SAE reporting requirements.

### 9.2.2 Procedures for reporting SAEs

If an SAE is reported, UCB must be informed within 24 hours of receipt of this information by the site (see contact information for SAE reporting listed in the SAE Reporting section at the front of the protocol). The Investigator must forward to UCB (or its representative) a duly

completed “Investigator SAE Report Form for Development Drug” (SAE report form) provided by UCB, even if the data are incomplete, or if it is obvious that more data will be needed in order to draw any conclusions. Information recorded on this form will be entered into the global safety database.

An Investigator SAE report form will be provided to the Investigator. The Investigator SAE Report form must be completed in English.

It is important for the Investigator, when completing the SAE report form, to include the assessment as to a causal relationship between the SAE and the IMP administration. This insight from the Investigator is very important for UCB to consider in assessing the safety of the IMP and in determining whether the SAE requires reporting to the regulatory authorities in an expedited manner.

Additional information (eg, autopsy or laboratory reports) received by the Investigator must be provided within 24 hours. All documents in the local language must be accompanied by a translation in English, or the relevant information included in the same document must be summarized in the Investigator SAE report form.

The Investigator is specifically requested to collect and report to UCB (or its representative) any SAEs (even if the Investigator is certain that they are in no way associated with the IMP), up to 30 days from the end of the study for each subject, and to also inform participating subjects of the need to inform the Investigator of any SAE within this period. Serious AEs that the Investigator thinks may be associated with the IMP must be reported to UCB regardless of the time between the event and the end of the study.

Upon receipt of the SAE report form, UCB will perform an assessment of expectedness of the reported SAE. The assessment of the expectedness of the SAE is based on the IB.

### **9.2.3 Follow up of SAEs**

An SAE should be followed until it has resolved, has a stable sequelae, the Investigator determines that it is no longer clinically significant, or the subject is lost to follow up. Further details regarding follow up of PDILI events is provided in [Section 9.7.1.4](#).

Information on SAEs obtained after clinical database lock will be captured through the PS database without limitation of time.

## **9.3 Immediate reporting of AEs**

The following AEs must be reported immediately:

- SAE: AE that the Investigator classifies as serious by the definitions in [Section 9.2.1](#) regardless of causality
- Suspected transmission of an infectious agent via a medicinal product
- AEs of special interest as defined in [Section 9.5](#)

## **9.4 Anticipated SAEs**

The following Anticipated SAEs ([Table 9–1](#)) are anticipated to occur in the population studied in this protocol at some frequency that is independent of drug exposure. This original list will

remain in effect for the duration of the protocol. Note that listed events will not be regarded as anticipated SAEs if they are life-threatening or if they result in the death of the study subject.

This list does not change the Investigator’s obligation to report all SAEs (including Anticipated SAEs) as detailed in [Section 9.2.2](#).

**Table 9–1: Anticipated SAEs for the population of subjects with moderate to severe chronic plaque psoriasis**

MedDRA® system order class	MedDRA preferred term
Skin and subcutaneous tissue disorders	Any psoriatic condition HLT
Musculoskeletal and connective tissue disorders	Psoriatic arthropathy

HLT=high level term; MedDRA=Medical Dictionary for Regulatory Activities; SAE=serious adverse event

Note: Exception: Listed events will not be regarded as anticipated SAEs if they are life-threatening or if they result in the death of the study subject.

### 9.5 Adverse events of special interest

An AE of special interest is any AE that a regulatory authority has mandated be reported on an expedited basis, regardless of the seriousness, expectedness, or relatedness of the AE to the administration of a UCB product/compound.

Potential Hy’s Law, defined as  $\geq 3 \times \text{ULN}$  ALT or AST with coexisting  $\geq 2 \times \text{ULN}$  total bilirubin in the absence of  $\geq 2 \times \text{ULN}$  ALP, with no alternative explanation for the biochemical abnormality, must ALWAYS be reported to UCB as an AE of special interest (ie, without waiting for any additional etiologic investigations to have been concluded). Follow-up information should then be reported if an alternative etiology is identified during investigation and monitoring of the subject.

### 9.6 Adverse events for special monitoring

UCB has identified AEs for special monitoring (AESM). An AESM is an AE or safety topic for which special monitoring, additional data collection activities, and/or enhanced signal detection activities (within UCB), are considered appropriate. Identified AESM can be of particular interest based on findings from the IMP clinical program to date, potential risks generally associated with biologic immunomodulators, or comorbidities and risk factors prevalent in the study population.

Adverse events for special monitoring for this study include: serious infections (including opportunistic infections and TB; see [Section 9.8.1](#)), cytopenias, hypersensitivities, suicide ideation or behavior (assessed using the C-SSRS; see [Section 9.8.6](#)), depression and anxiety (assessed using the HADS; see [Section 12.4](#)), major cardiovascular events, and liver function test changes/enzyme elevations (ALT, AST, bilirubin; see [Section 9.7.1](#)), malignancies, and inflammatory bowel diseases.

### 9.7 Laboratory measurements

Clinical laboratory assessments consist of serum chemistry, hematology, and urinalysis. A centralized laboratory will be used to supply all laboratory test supplies and analyze all blood and urine samples for hematology, biochemistry, and urinalysis measurements. Any unscheduled

laboratory testing should also be collected using the central laboratory. Laboratory parameters to be measured are listed in [Table 9–2](#).

Specific details regarding the handling and processing of serum chemistry, hematology, and urinalysis samples are provided in the study laboratory manuals.

**Table 9–2: Laboratory measurements**

Hematology	Chemistry	Urinalysis
Basophils	Calcium	Albumin
Eosinophils	Chloride	Bacteria
Lymphocytes	CRP	Crystals
Atypical lymphocytes	Magnesium	Glucose
Monocytes	Potassium	pH
Neutrophils	Sodium	RBC
Hematocrit	Glucose	WBC
Hemoglobin	BUN	Urine dipstick for pregnancy testing a
MCH	Creatinine	
MCHC	ALP	
MCV	AST	
Platelet count	ALT	
RBC count	GGT	
WBC count	Total bilirubin	
	LDH	
	Total cholesterol	
	Serum pregnancy testing a	
	Serum FSH b (Screening)	

ALP=alkaline phosphatase; ALT=alanine aminotransferase; AST=aspartate aminotransferase; BUN=blood urea nitrogen; CRP=C-reactive protein; FSH=follicle stimulating hormone; GGT=gamma glutamyltransferase; LDH=lactate dehydrogenase; MCH=mean corpuscular hemoglobin; MCHC=mean corpuscular hemoglobin concentration; MCV=mean corpuscular volume; RBC=red blood cell; WBC=white blood cell

a Pregnancy testing will consist of serum testing at the SFU Visit. The pregnancy test will be urine at all other visits and will be performed locally.

b The FSH test should only be performed on postmenopausal females who have been postmenopausal for  $\geq 1$  year and last menstrual cycle occurred  $< 2$  year ago.

Assessments of PK variables are described in [Section 10](#). Assessments of immunological variables are described in [Section 11](#).

### 9.7.1 Evaluation of PDILI

The PDILI IMP discontinuation criteria for this study are provided in [Section 6.3.1](#), with the accompanying required follow-up investigation and monitoring detailed below. All PDILI events

must be reported as an AE and reported to the study site and Sponsor within 24 hours of learning of their occurrence. Any PDILI event that meets the criterion for potential Hy's Law must be reported as an AE of special interest (see [Section 9.5](#)), and, if applicable, also reported as an SAE (see [Section 9.2.1](#)).

Evaluation of PDILI consists of the diagnostic testing and continued monitoring included in [Table 9-3](#) (specific tests dependent on laboratory results and corresponding symptoms) and consultation with a local hepatologist (if applicable; discussed in [Section 9.7.1.1](#)). The local hepatologist is the expert usually consulted by the treating physician for assessment and management of potential hepatic disease. This would usually be a hepatologist, but may be a gastroenterologist. Additional investigation and monitoring may be required and adapted based on the diagnosis after the cause of the liver injury/abnormality is confirmed (details in [Section 9.7.1.4](#)).

The results of all monitoring, including laboratory testing and other testing, should be made available to the study site and Sponsor.

All initial tests resulting in abnormal hepatic laboratory values need to be repeated, but appropriate medical action must not be delayed waiting for the repeat result.

If tests are done locally for more rapid results, a concurrent sample should also be sent to the central laboratory whenever possible. Medical care decisions are to be made initially using the most rapidly available results and a conservative approach must be taken if the results from the 2 laboratory tests are significantly different. Data from the local and central laboratory are to be recorded on the applicable eCRF pages.

When IMP is discontinued, all concomitant medications and herbal supplements that are not medically necessary should also be discontinued. In these cases, the Investigator should also consider dose reduction for medically necessary concomitant medication and consider changing any medically required concomitant medication known to be hepatotoxic to a suitable alternative.

When IMP is stopped due to PDILI (as described in [Section 6.3.1](#)), IMP must be permanently discontinued even if a subsequent alternative diagnosis fully explains the hepatic findings.

Rechallenge with a substance potentially causing drug-induced liver injury is dangerous, may be fatal, and must not occur.

[Table 9-3](#) summarizes the approach to investigate PDILI.

**Table 9-3: Required investigations and follow-up for PDILI**

Laboratory value		Symptoms a of hepatitis or hypersensitivity	Immediate		Follow up	
ALT or AST	Total bilirubin		Consultation requirements	Actions	Testing	Evaluation
≥3xULN	≥2xULN b	NA	Hepatology consult. c Medical Monitor must be notified within 24 hours (eg, by laboratory alert) and subject discussed with Medical Monitor ASAP.	Immediate, permanent IMP discontinuation.	Essential. Must have repeat liver chemistry values and additional testing completed ASAP (see Section 9.7.1.3 ); recommended to occur at the site with HCP.	Monitoring of liver chemistry values at least twice per week until values normalize, stabilize, or return to within baseline values. d
≥3xULN	NA	Yes				
≥5xULN	NA	NA	Need for hepatology consult to be discussed (required if ALT or AST ≥8xULN). Medical Monitor must be notified within 24 hours (eg, by laboratory alert) and subject discussed with Medical Monitor ASAP.			

**Table 9-3: Required investigations and follow-up for PDILI**

Laboratory value		Symptoms a of hepatitis or hypersensitivity	Immediate		Follow up	
ALT or AST	Total bilirubin		Consultation requirements	Actions	Testing	Evaluation
≥3xULN (and ≥2x baseline) and <5xULN (and ≥2x baseline)	<2xULN	No	Discussion with Medical Monitor required. Consider need for hepatology consult if there is no evidence of resolution (see Follow up requirements). c	Further investigation – immediate IMP discontinuation not required (see Section 9.7.1.2 ). IMP discontinuation required if any of the following occur: 
 
• Subject cannot comply with monitoring schedule.
 
• Liver chemistry values continue to increase.
 
• Liver chemistry values remain ≥3xULN (and ≥2x baseline) after 2 weeks of monitoring without evidence of resolution.
 
	Essential: Every attempt must be made to have repeat liver chemistry values and additional testing completed within 48 hours at the site with HCP (see Section 9.7.1.3 ).	Monitoring of liver chemistry values at least twice per week for 2 weeks. d 
 
• Immediate IMP discontinuation required if liver chemistry values continue to increase.
 
 After 2 weeks of monitoring liver chemistry values: 
 
• Discontinue IMP if levels remain ≥3xULN (and ≥2x baseline) without evidence of resolutiond
 
• Continue to monitor until values normalize, stabilize, or return to within baseline values.d
 

ALT=alanine aminotransferase; ASAP=as soon as possible; AST=aspartate aminotransferase; HCP=healthcare practitioner; IMP=investigational medicinal product; NA=not applicable; PDILI=potential drug-induced liver injury; ULN=upper limit of normal

a Hepatitis symptoms include fatigue, nausea, vomiting, and right upper quadrant pain or tenderness; hypersensitivity symptoms include eosinophilia (>5%), rash, and fever (without clear alternative cause).

b If the subject also has ≥2xULN alkaline phosphatase, the possibility of an indication of biliary obstruction should be discussed with the Medical Monitor.

c Details provided in [Section 9.7.1.1](#). The local hepatologist is the expert usually consulted by the treating physician for assessment and management of potential hepatic disease. This would usually be a hepatologist, but may be a gastroenterologist.

d Unless an alternative monitoring schedule is agreed by the Investigator and UCB responsible physician. Determination of stabilization is at the discretion of the Investigator in consultation with the hepatologist (as applicable) and UCB responsible physician, as needed.

### **9.7.1.1 Consultation with Medical Monitor and local hepatologist**

Potential drug-induced liver injury events require notification of the Medical Monitor within 24 hours (eg, by laboratory alert), and the subject must be discussed with the Medical Monitor as soon as possible. If required, the subject must also be discussed with the local hepatologist. The local hepatologist is the expert usually consulted by the treating physician for assessment and management of potential hepatic disease. This would usually be a hepatologist, but may be a gastroenterologist. If determined necessary, this discussion should be followed by a full hepatology assessment (see [Section 9.7.1.3](#)) and SAE report (if applicable).

### **9.7.1.2 Immediate action: determination of IMP discontinuation**

All PDILI events require immediate action, testing, and monitoring.

The immediate action is dependent on the laboratory values and symptoms of hepatitis or hypersensitivity and ranges from continuation of IMP (followed by immediate investigation) to immediate and permanent discontinuation (see [Section 6.3.1](#) and [Table 9-3](#) for details).

When IMP is discontinued, all concomitant medications and herbal supplements that are not medically necessary should also be discontinued. The Investigator should also consider dose reduction for medically necessary concomitant medication and consider changing any medically required concomitant medication known to be hepatotoxic to a suitable alternative.

### **9.7.1.3 Testing: identification/exclusion of alternative etiology**

The measurements and additional information required for the assessment of PDILI events when there is a reasonable possibility that they may have been caused by the IMP include, but are not limited to, those listed in [Table 9-4](#) (laboratory measurements) and [Table 9-5](#) (additional information). Results of the laboratory measurements and information collected are to be submitted to the Sponsor on the corresponding eCRF. If the medical history of the subject indicates a requirement for other assessments not included below, these additional assessments should be completed and submitted, as applicable.

All blood samples should be stored, if possible. If tests are done locally for more rapid results, a concurrent sample must also be sent to the central laboratory.

The laboratory measurements to be assessed are presented in [Table 9-4](#).

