**Table 9-4: PDILI laboratory measurements**

Virology-related	Hepatitis A IgM antibody
	HBsAg
	Hepatitis E IgM antibody
	HBcAb-IgM
	Hepatitis C RNA
	Cytomegalovirus IgM antibody
	Epstein-Barr viral capsid antigen IgM antibody (if unavailable, obtain heterophile antibody or monospot testing)
Immunology	Anti-nuclear antibody (qualitative and quantitative)
	Anti-smooth muscle antibody (qualitative and quantitative)
	Type 1 anti-liver kidney microsomal antibodies (qualitative and/or quantitative)
Hematology	Eosinophil count
Urinalysis	Toxicology screen a
Chemistry	Amylase
	If total bilirubin $\geq 1.5 \times \text{ULN}$ , obtain fractionated bilirubin to obtain % direct bilirubin
	Serum CPK and LDH to evaluate possible muscle injury causing transaminase elevation
Additional	Prothrombin time/INR b
	Serum pregnancy test
	PK sample

ALT=alanine aminotransferase; CPK=creatine phosphokinase; HBcAb-IgM=hepatitis B core antibody-IgM; HBsAg=hepatitis B surface antigen; IgM=immunoglobulin M; INR=international normalized ratio; LDH=lactate dehydrogenase; PDILI=potential drug-induced liver injury; PK=pharmacokinetic; RNA=ribonucleic acid; ULN=upper limit of normal

a For detecting substances (ie, amphetamines, benzodiazepines, opioids, marijuana, cocaine, phencyclidine, and tricyclic antidepressants), additional tests may be performed based on the Investigator's medical judgment and patient's history.

b Measured only for subjects with ALT  $> 8 \times \text{ULN}$ , elevations in total bilirubin, and symptoms of hepatitis or hypersensitivity. Hepatitis symptoms include fatigue, nausea, vomiting, and right upper quadrant pain or tenderness; hypersensitivity symptoms include eosinophilia ( $> 5\%$ ), rash, and fever (without clear alternative cause).

Additional information to be collected is presented in [Table 9-5](#).

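### The liver work-up section adds a drug-causality condition that the rest of the PDILI plan lacks, and the PT/INR footnote omits some subjects who need a hepatology consult

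*Protocol*

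**What the plan says.** **Scope of the work-up.** Section 9.7.1.2 states: "All PDILI events require immediate action, testing, and monitoring". Table 9-3 marks testing as essential in its first row ("Must have repeat liver chemistry values and additional testing completed ASAP") and again in its lowest tier ("Every attempt must be made to have repeat liver chemistry values and additional testing completed within 48 hours"). Both entries send the reader to Section 9.7.1.3 for the content, and neither mentions causality. Section 9.7.1 describes the tests as "specific tests dependent on laboratory results and corresponding symptoms". Section 9.7.1.3 then presents the items in Tables 9-4 and 9-5 as those needed for PDILI events "when there is a reasonable possibility that they may have been caused by the IMP". Its heading says that the testing is there to identify or exclude another etiology.

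**PT/INR.** Footnote b of Table 9-4 reads "Measured only for subjects with ALT" above 8xULN, "elevations in total bilirubin, and symptoms of hepatitis or hypersensitivity". Table 9-3 lists a hepatology consult for ALT or AST at or above 3xULN with bilirubin at or above 2xULN. For the row at or above 5xULN it says "Need for hepatology consult to be discussed (required if ALT or AST ≥8xULN").

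**The concern.** Viral serology, autoantibodies, the toxicology screen and CPK are the evidence on which a causality judgement rests. If they are required only once IMP causation is thought reasonably possible, a site that presumes another cause could read Section 9.7.1.3 as not requiring them, and the presumption would go unchecked.

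The PT/INR footnote is a separate matter. Its conditions differ from the consult trigger in three ways: it names ALT but not AST, it uses more than 8xULN where Table 9-3 uses at least 8xULN, and it joins three conditions with a conjunction. A subject could have the drug stopped permanently and be sent to a hepatologist while the listed panel contains no INR.

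What is at stake is the completeness of the work-up in a study whose primary objective is safety and which names liver enzyme changes as an event for special monitoring (Protocol 9.6).

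**Working it through.** **Part 1: the texts side by side**

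| Protocol text | Which events get the testing | Causality condition |
|---|---|---|
| 6.3.1 | PDILI as defined by ALT, AST, bilirubin and symptoms; evaluation per 9.7.1 | none |
| 9.7.1 | tests chosen by laboratory results and symptoms | none |
| 9.7.1.2 | all PDILI events | none |
| Table 9-3, first row and lowest tier | essential; content in 9.7.1.3 | none |
| 9.7.1.3 | items in Tables 9-4 and 9-5 | IMP causation reasonably possible |

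The first four lead to the fifth, and only the fifth carries a condition. This is an inconsistency rather than an express waiver: 9.7.1.3 does not restrict the tests to such events in so many words, and it closes with an unconditional pointer to Table 9-4.

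**Part 2: two single cases**

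- Footnote b read jointly: ALT 4xULN, bilirubin 3xULN, no symptoms. Section 6.3.1 requires permanent discontinuation and Table 9-3 requires a consult. Footnote b lists no INR.
- Footnote b read as alternatives: ALT 6xULN, AST 10xULN, normal bilirubin, no symptoms. Table 9-3 requires a consult because AST is at least 8xULN. Footnote b lists no INR.

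**Part 2: a grid**

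The grid levels are my choice: ALT and AST each at 1, 4, 6, 8, 10xULN; bilirubin at 0.8, 1.5, 3xULN (elevated means above ULN); symptoms absent or present.

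- All patterns: 5 × 5 × 3 × 2 = 150. PDILI (ALT or AST at least 3xULN): 24 ALT/AST pairs × 6 = 144.
- Consult required: 16 pairs have a maximum of at least 8xULN, giving 16 × 6 = 96. The other 8 pairs need bilirubin at least 2xULN or symptoms, which is 4 of 6 combinations, giving 8 × 4 = 32. Total 96 + 32 = 128.
- The consult for the symptoms row rests on reading blank cells in Table 9-3 as merged with the row above. Without that reading: 96 + 8 × 2 = 112.
- Footnote b, joint: ALT 10 (5 AST levels) × 2 elevated bilirubin levels × symptoms present = 10.
- Footnote b, alternatives: the consult patterns missed have ALT at most 8xULN, normal bilirubin, no symptoms and a maximum of at least 8xULN. That is 16 − 5 = 11, leaving 128 − 11 = 117, or 112 − 11 = 101.

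| INR listed in | Joint | Alternatives | Proposed footnote |
|---|---|---|---|
| 128 consult patterns | 10 | 117 | 128 |
| 112 (blank cells not merged) | 10 | 101 | 112 |
| 144 PDILI patterns | 10 | 125 | 136 |
| 48 with ALT or AST ≥3xULN and bilirubin ≥2xULN | 5 | 48 | 48 |

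A second grid (ALT and AST at 1, 3, 5, 8, 8.1, 10xULN; bilirubin at 1, 1.5, 2, 3xULN) gives 264 consult patterns, with 228 missed jointly and 15 missed as alternatives. The counts move with the grid; the existence of a gap on both readings does not.

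**The case against.** On part 1, the clause can be read as merely describing what PDILI means. A reasonable possibility is a low bar, and in a dosed subject with no results yet it will usually be met. Section 6.3.1 also requires evaluation as set out in 9.7.1 and keeps subjects in the study until the investigation is complete. Section 9.7.1.1 requires Medical Monitor notification within 24 hours and a discussion of the subject. All of this makes a skipped work-up unlikely. It does not settle which text governs, because 6.3.1 and 9.7.1 both lead back to the section carrying the condition. Nor do 6.3.1 and Table 9-3 define PDILI by causality, so the clause adds something.

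On part 2, nothing in the protocol says that the INR and consult triggers must match. Aligning them is a recommendation, and that point stands. The omitted subjects see a hepatologist, who may order an INR, since 9.7.1.3 says its list is not exhaustive. Against that, the footnote's restrictive opening tells sites the opposite.

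The grid is arbitrary and ignores the baseline multiple in the lowest tier. Three of the 11 patterns (ALT 8 with AST 1, 4 or 6) arise only because the grid sets ALT at exactly 8xULN. These criticisms limit the counts, not the logic. It is also true that sample size, error rates and the primary exposure-adjusted rates do not change, and that subjects with Grade 3 laboratory values are withdrawn in any case (Protocol 6.3, criterion 10).

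**Conclusion.** Both parts hold. Section 9.7.1.3 conflicts with 9.7.1.2 and Table 9-3 on which PDILI events get the etiology tests. Footnote b leaves PT/INR off the list for some subjects with a required hepatology consult, however it is read.

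The size of the second gap depends on the reading. Taken jointly, which is the plain wording, it is wide and includes subjects with combined transaminase and bilirubin elevation whose IMP is permanently stopped. Taken as alternatives, it shrinks to AST at least 8xULN with ALT at most 8xULN, or ALT exactly 8xULN, in both cases with normal bilirubin and no symptoms.

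The conclusion assumes that elevated bilirubin means above ULN. It does not need the merged-cell reading of Table 9-3. Potential Hy's Law reporting (9.5), discontinuation (6.3.1, 9.7.1) and the SAP liver table (Table 14-3) are untouched. The change is worth making because it improves safety data at little cost, not because any planned estimate is wrong.

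**What to change.** 1. In Section 9.7.1.3, delete "when there is a reasonable possibility that they may have been caused by the IMP", so that Tables 9-4 and 9-5 apply to every PDILI event.
2. Replace footnote b of Table 9-4 with three separate triggers for PT/INR: (a) ALT or AST ≥8xULN; or (b) ALT or AST ≥3xULN with total bilirubin above ULN; or (c) ALT or AST ≥3xULN with hepatitis or hypersensitivity symptoms.

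The new footnote covers every required-consult case, because the consult triggers are (a), a stricter form of (b), and (c). It removes no INR listed now. Every PDILI tier in 6.3.1 starts at ALT or AST ≥3xULN, so a PDILI subject with ALT above 8xULN, raised bilirubin or symptoms falls under (a), (b) or (c) respectively.

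The cost is one deleted clause, one reworded footnote and a few more blood tests in rare cases. On the grid, 136 − 125 = 11 more patterns get an INR than under the alternatives reading and 136 − 10 = 126 more than under the joint reading. The 8 PDILI patterns still without one have a maximum ALT or AST of 4 or 6xULN, normal bilirubin and no symptoms, where Table 9-3 does not require a consult. All the tests are already in Table 9-4, and the SAP needs no change.
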